Data management	
Open Data Kit (ODK) system will be used as data collection instrument. We will collect data on patients' characteristics, antimicrobial prescription status, the frequency of use of the antimicrobial prescribing guidelines (both paper-based and mobile app), AMS knowledge level of prescribers, acceptability of the guidelines and the cost of antimicrobial prescriptions in both groups.
 
All data will be kept securely, protected by password access with automatic daily backup.

Statistical analysis	A logistic mixed-effects regression model will be used to compare the proportion of antimicrobial prescription adherence measured cross-sectionally at month 0, 4, 8, 12 and month 16 after introduction of prescribing guidelines delivered by mobile phone application versus paper-based. The model will compare all wedges in the intervention from month 4 to month 16 with all wedges in the reference arm from month 0 to month 12. The duration of exposure of each hospital to the reference or intervention arm will be included in the model as interaction term with the study arm in order to assess whether the duration of exposure is the effect modifier. The model will consider the correlation among the outcomes' measurements from the same hospital (cluster) by adjusting for clustering in the model. Odds ratios and the corresponding confidence intervals will be obtained and reported.
Ethics	University of Health Sciences, Vientiane, Lao PDR and Oxford Tropical Ethics Committee (OxTREC), University of Oxford, United Kingdom

Trial insurance	Provided by University of Oxford
Dissemination	1/ Quarterly and annual reports (PPS dashboard and paper report) to participating hospitals, Lao Ministry of Health 2/ Publication in national and international journals 3/ Oral presentation/poster in both national and international levels
Sponsor	University of Oxford
Funder	Wellcome Trust of Great Britain

I. Introduction

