3.3 Sample size and power calculation

A PPS of hospital antimicrobial use in four general hospitals in Laos in 2017 showed 13% compliance to Lao treatment guidelines (LOMWRU unpublished data) but previous guidelines did not contain much information on antibiotic prescribing, therefore reliable baseline data are lacking.

The sample size of 6 hospitals was estimated assuming 30% of antimicrobial prescription adherence with the paper-based prescribing guideline (reference), and assuming 0.05 intra-cluster correlation coefficient. This will have 80% of power of the test to be able to detect 15% minimum difference after introduction of the mobile phone app prescribing guidelines at 0.05 significant level.

This will be a 3-step trial with one baseline measurement after introduction of the paper-based prescribing guidelines. The outcomes will be measured every four months. These will give four outcomes measurements in total (excluding baseline measurement at start), until the trial

completes at month 16.

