3.4 Randomization and blinding

Six participating hospitals have been divided into 3 pairs based on the geographical location and convenience for conducting the surveys. The first paired hospitals include two provincial hospitals from the north of Laos (Luang Namtha and Xiengkhuang), the second pair includes hospitals in the center (Mahosot Hospital-central referral hospital and Vientiane provincial hospital which is 80 km from the center of the capital to the north). The third pair includes two provincial hospitals from the south of Laos (Savannakhet and Salavan).

As there are only 3 orders to be assigned, clusters will be randomly assigned to one of three start dates using a simple random sampling, to have access to the study intervention. Three paired hospitals (LNT+XK, MS+VTP and SVK+SV) will be written on three different paper slips (similar paper size and paper texture). All slips will be folded to the same size and put in the non-transparent container, covered firmly and mixed well. A person who is not related to the study will be asked to pick up the paper slip one by one and read out to the PI and a co-investigator. Simple random sampling processes will be performed before the start of the project and the order of each paired hospital to intervention introduction will be recorded. At month 4 after the start of the project, the intervention will be introduced to the first selected paired hospital, then every four months each pair of hospitals will be rolled out from the reference phase to the intervention phase until all have started the intervention. This will give 1:1 ratio of intervention vs reference period of observation (figure 2). We will therefore be able to compare the effects of the reference and intervention over a reasonable period of time. Neither hospitals nor investigators will be blinded to the introduction of the intervention.

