Most recommendations are for empiric treatment. For pathogens and syndromes for which Lao data are available, common causative pathogens and their antimicrobial susceptibilities are provided as a guide. This guideline also refers to some specific Lao treatment guidelines (e.g. Dengue guideline for diagnosis and treatment, Lao PDR or National Guidelines for the Use of Antiretroviral Therapy in Adults and Children) to avoid duplication.

Common and important infectious diseases are arranged by involved organ systems. Each infectious disease section includes causative pathogen (s) of the diseases, choices of antimicrobial regimen (primary and alternative), doses, duration and important notes on allergy or toxicity or to help guide treatment.

b. Reference phase

Study duration will be divided into two parts, reference and intervention phases. At the start (month 0), a point prevalence survey (PPS) on hospital antimicrobial use will be performed (more details on conduct of PPS are given in following section) to collect baseline data before introducing paper-based guidelines. The participating hospitals will receive a report of the PPS findings within one month of the survey (Appendix A4).

After PPS, all medical doctors of each participating hospital will be asked to complete an AMS knowledge survey (Appendix A5) and pre-prescribing guidelines survey (Appendix A9). Then, paper-based prescribing guidelines in both adult and paediatric versions (one adult guideline and one paediatric guideline) will be distributed to all doctors at participating hospitals, followed by guideline introductory session of the guidelines (Appendix A6). This session will not cover how to diagnose infectious diseases or prescribe antimicrobials but how to use these guidelines.

After introduction of the paper-based guidelines, all six hospitals will be formally included in the reference period. PI and research team will not become involved with any antimicrobial prescribing decisions of local prescribers at participating hospitals for individual patients. There will be contact details of the PI in the guidelines in case any prescribers need more clarification on the guidelines. A prescriber feedback survey on the paper-based version will be performed just before each paired hospital enters to the intervention phase (month 4, month 8 and month 12 after introduction of the paper-based prescribing guidelines).

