After the first paired hospital is randomly selected to have access to the mobile phone app prescribing guidelines at month 4, the second pair of hospitals will be randomly selected to have access to the mobile phone app at month 8, and the last pair of hospitals will have access to a mobile phone app at month 12 (Figure 2).

The order of activities at the start of the project are listed below (these activities will be applied to all six hospitals, one by one):

1. PPS on hospital antimicrobial use for all 6 hospitals (Appendix A1, A2 and A3)
2. AMS knowledge survey (Appendix A5)
3. Pre-prescribing guidelines survey (Appendix A9)
4. Access to paper prescribing guidelines for all 6 hospitals
5. Introductory session to paper prescribing guidelines (Appendix A6)
6. PPS reports (Appendix A4)

Activities in the reference phase after the start of the project (month 0) until the last paired hospital is assigned to the intervention (month 12) are listed below:

1. PPS on hospital antimicrobial use (Appendix A1, A2 and A3)
2. PPS reports (Appendix A4)

c. Intervention phase

c.1 Antimicrobial Prescribing guidelines mobile phone application (MicroGuide)

Both paediatric and adult antimicrobial prescribing guidelines will be transferred to [MicroGuide](#); which is a medical guideline application. MicroGuide was launched in 2013 and has been adopted by 114 medical organizations, with more than 100,000 users in 173 countries. MicroGuide is an offline application, free-of-charge for the individual users. The app can monitor the number of users and which guidelines are being accessed.

The app will be installed to the personal smart phones of local physicians by the PI. The project will not provide a smart phone to any physician without one (approximately <10% of physicians in provincial hospitals– unpublished data). The contents of the mobile app guidelines will be the same as the paper version but using hyperlinks to information, rather than displaying it as in paper guidelines. Both mobile app and paper guidelines will be available in Lao and English languages.

c.2 Antimicrobial stewardship (AMS) training

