This survey questionnaires will be in Lao language. The survey will provide information on the level of knowledge of rational antibiotic prescribing of prescribers before and after having access to paper prescribing guidelines and the app prescribing guidelines at different time points. For more details on what questions will be asked, see Appendix A5. *Antibiotic stewardship knowledge survey*.

Each survey will include 8 questions in total. The 8 questions will be randomly selected (simple random sampling – using a computer-generated random allocation sequence) from a set of questions in Appendix A5. The answers to all questions are in the guidelines.

Maximum 10 minutes will be requested to complete 8 questionnaires. The questionnaires will be multiple answers. There is no need to put the name of responders to the survey form but age, graduated year, department and speciality are needed. The survey will be conducted in the same day as introduction to the guidelines (paper (month 0)/app), introductory session of the guidelines (paper (month 0)/app), pre-prescribing guidelines survey (month 0), AMS training (only for those firstly enter to intervention period). Complete survey forms will be collected by the research team before starting the introductory session of the guidelines (paper (month 0)/app).

Pre-prescribing guidelines survey

The aim of conducting a pre-prescribing guidelines survey is to understand how prescribers prescribe antimicrobials and how much they use any prescribing guidelines in their routine work. This will provide some explanation as to what prescribers think about the provided prescribing guidelines. The survey will be performed once at the beginning of the study (month 0) after the first round of PPS and before introduction of the paper prescribing guidelines. Survey form (Appendix A9. *Pre-prescribing guidelines survey*) will be distributed to all prescribers at each study hospital and collecting back by the research team in the same day. The survey form contains 6 questions and it will take 5 minutes maximum to complete the survey.

Prescriber feedback survey on paper-based prescribing guidelines

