measured cross-sectionally at month 0, 4, 8, 12 until month 16 after introduction of prescribing guidelines by mobile phone application versus paper-based (30). The model will compare all wedges in the intervention from month 4 to month 16 with all wedges in the reference arm from month 0 to month 12. The duration of exposure of each hospital to the reference or intervention arm will be included in the model as interaction term with the study arm in order to assess whether the duration of exposure is the effect modifier. The model will consider the correlation among the outcome's measurements from the same hospital (cluster) by adjusting for clustering in the model. Odds ratios and the corresponding confidence intervals will be obtained and reported. Tests of significance will be performed at 5% level. Analyses will be done using Stata 15.0 or higher. Likert scale analysis will be used to evaluate prescriber satisfaction with/ acceptability of paper-based compared to mobile phone app delivered antimicrobial prescribing guidelines. The satisfaction/acceptability scale will be assigned in six categories, including strongly agree=5, agree=4, neutral=3, disagree=2 and strongly disagree=1, no opinion/not use=0. Mann-Whitney test will be used to assess the differences between paper-based population and mobile phone app population. AMS knowledge level of prescribers will be assessed using questionnaires based on information in the prescribing guidelines. The overall proportion of correct answers in each time point will be compared (baseline, after paper-based guidelines (before AMS training and introduction of mobile phone app guidelines) and after AMS training and introduction of mobile phone app guidelines). Other factors such as extra AMR training program from hospital/MoH/other organizations, level of education and specialties of prescribers will also be taken into account.

Cost of antibiotic therapy will be calculated from the start date of treatment to the survey day. The unit costs for the antibiotics will be obtained from the [International Medical Product Price Guide](#).

Antibiotic defined daily dose (DDD) will be calculated using data (antibiotic agent, start date, dose and DDD of each antibiotic from www.whooc.no) from PPS in both IPD and OPD. Antimicrobial cost data from participating hospitals will also be collected each hospital pharmacy for comparison with international cost.

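### The month-0 survey is taken before the trial's paper guideline is issued, yet the primary analysis can be read as counting it as paper-guideline data; its role must be fixed.

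*Combined protocol and SAP*

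**What the plan says.** **Timing of the month-0 survey.** Section 3.5 (Reference phase) says that it is done "to collect baseline data before introducing paper-based guidelines". The same section adds: "After introduction of the paper-based guidelines, all six hospitals will be formally included in the reference period". In the start-up list the survey is item 1 and "Access to paper prescribing guidelines for all 6 hospitals" is item 4. Section 3.7 places the pre-prescribing survey "after the first round of PPS and before introduction of the paper prescribing guidelines", which gives the same order. Figure 2 shows only survey and report at month 0; paper first appears in the month-4 column.

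**The conflicting sentence.** Section 3.3 states: "This will be a 3-step trial with one baseline measurement after introduction of the paper-based prescribing guidelines". It then counts four outcome measurements with baseline left out.

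**Analysis.** The synopsis models adherence "measured cross-sectionally at month 0, 4, 8, 12 and month 16", and the Statistical analysis section gives the same months. Both describe the contrast as "all wedges in the intervention from month 4 to month 16 with all wedges in the reference arm from month 0 to month 12". Named terms are an adjustment for hospital and an interaction of arm with duration of exposure. No survey-month term is named, and the form of duration (linear or categories) is not given.

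**Balance.** Section 3.4: "This will give 1:1 ratio of intervention vs reference period of observation".

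**The concern.** The primary question is app versus paper. At month 0 no doctor holds the trial's guideline, but section 3.6 scores adherence against the guideline provided. Month 0 is therefore a third condition. A two-arm model that lists it as an outcome, with a reference arm starting at month 0, leaves it no evident place except paper.

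Any rise in adherence from before the guideline to paper would then pull the reference average down and be credited in part to the app. The arm-by-duration term could also read that rise as paper improving with exposure, and so report an effect modification that does not exist.

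**Working it through.** **1. The plan's own counts.** From Figure 2, with six hospitals in three pairs and the app first reflected in the surveys at months 8, 12 and 16:
- App hospital-surveys: 2 × (3 + 2 + 1) = 12.
- Paper hospital-surveys, months 4 to 12: 2 × (1 + 2 + 3) = 12.
- Month-0 hospital-surveys: 6.

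Without month 0 the ratio is 12 v 12 and there are four outcome surveys, as sections 3.4 and 3.3 say. With month 0 as paper it is 18 v 12 and there are five. Counted in time, each condition has 2 × (4 + 8 + 12) = 48 hospital-months, so 1:1 also holds for periods.

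The 80% power in section 3.3 cannot be reproduced, because no number of prescriptions per hospital-survey is given.

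**2. Inputs for the bias.** Paper adherence is 30% (section 3.3). The app is set to 30% as well, so the true odds ratio (OR) is 1.00. Month-0 adherence is unknown. It is varied over 25%, 20% and 13%; the last is the 2017 survey figure in section 3.3, which was scored against older Lao guidelines and is illustrative only.

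**3. Pooled reference with month 0 coded as paper:** (6 × p0 + 12 × 30%) / 18.

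| Month-0 adherence p0 | Pooled reference | False gain | OR, arm + hospital |
|---|---|---|---|
| 30% | 30.0% | 0 | 1.00 |
| 25% | 28.3% | 1.7 points | 1.10 |
| 20% | 26.7% | 3.3 points | 1.20 |
| 13% | 24.3% | 5.7 points | 1.38 |

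The ORs come from a binomial model with hospital fixed effects (standing in for the random intercept), fitted to expected counts with equal hospital sizes. At 13% the false gain is 5.7 / 15 = 38% of the target difference, read as 15 percentage points. If the app truly moves adherence from 30% to 45%, the OR is (0.45/0.55) / (0.30/0.70) = 1.91, and this model returns 2.63.

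**4. The same data (no app effect, month 0 at 13%) under other model forms.**

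| Model | App OR |
|---|---|
| Arm + hospital, month 0 dropped | 1.00 |
| Month 0 kept, categorical survey month | 1.00 |
| Month 0 kept, linear month | 0.71 |
| Month 0 kept, arm × linear duration | 1.41, 0.96, 0.66 at 4, 8, 12 months |
| Month 0 kept, arm × categorical duration | 1.00 at 4, 8, 12 months |

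Categorical duration works because month 0 is the only survey with zero exposure and so gets its own level. With categorical months and a true OR of 1.91, the model recovers 1.91.

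**5. False-positive rates.** Section 1 gives 1,981 inpatient charts, 72% with an antimicrobial, in five hospitals: 1,981 × 0.72 / 5 = 285 per hospital-survey if that was one round, or 71 if four (the number of rounds is assumed). With 30 added as a low case, simulation of the arm-plus-hospital model with month 0 at 13% declares an inert app significant in 51%, 89% and 100% of trials at 30, 71 and 285 prescriptions. Leaving month 0 out gives 3% to 7%.

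**The case against.** The strongest reply is that the quoted comparison describes periods and not surveys. Read as survey months, an intervention arm starting at month 4 has no data: section 3.5 puts each pair's survey before app access, and Figure 2 has all six hospitals on paper at month 4. Read as periods, months 4 to 16 and months 0 to 12 are 12 months each, which fits the stated 12 months' exposure and the 1:1 ratio. Sections 3.3, 3.5 and 3.7 also call month 0 baseline. This shows that exclusion may well be intended. It does not settle the matter, because the month-0 survey is still listed as a modelled outcome and no coding is given for it.

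A second reply is that the ORs above 1.00 depend on model form. This stands: categorical months or categorical duration remove the bias with month 0 kept. But the plan states neither. It cites a methods paper for the model, and a citation does not specify a term. Categorical months are also a full cure only if the jump is common to all hospitals. An assumed between-hospital SD of 8 points in the jump would add about 1.7 points of SD to the app estimate, which is extra noise and not directional bias.

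Third, the 13% was scored against a different document, and section 3.3 itself says that reliable baseline data are lacking. This stands too, hence the range.

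A reader might also infer that hospitals had no guideline at all at month 0. They did: section 1 reports that 58 of 70 surveyed doctors used Lao treatment guidelines. Only the trial's prescribing guideline was absent.

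**Conclusion.** The contradiction on timing is firm: section 3.3 disagrees with section 3.5, section 3.7 and Figure 2. It is also firm that the plan models month 0 without saying which condition it belongs to.

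The bias is conditional. It needs month 0 coded as paper, no categorical survey-month effect, and duration omitted or linear. Under those choices, with no app effect and 30% on both formats, the OR is 1.10 to 1.38 for month-0 adherence of 25% down to 13%, and linear duration gives a false trend from 1.41 to 0.66 at 13%. The bias is zero if paper does not change adherence. A reader might conclude that the planned analysis will make an ineffective app look effective; the documents do not support that, because they leave each of these choices open. The point should still be settled before analysis, since it bears on the primary estimate and a natural reading of the text leads to the biased form.

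**What to change.** 1. State in the synopsis and in the Statistical analysis section that the month-0 survey is a pre-guideline baseline outside the app-versus-paper contrast. Either fit the primary model to months 4, 8, 12 and 16 (12 v 12 hospital-surveys), or give month 0 its own level for the period before the trial guideline. Use it descriptively for the change from before the guideline to paper.
2. Name categorical survey-month effects in the primary model. A linear month term is not a substitute (OR 0.71 in the check above).
3. State how duration of exposure enters the model.
4. Reconcile the baseline sentence in section 3.3 with section 3.5 and Figure 2.

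The cost is wording and a little precision. By a Hussey-Hughes calculation with period effects (30% v 45%, intra-cluster correlation 0.05, two-sided 5%), dropping month 0 moves power from 96% to 94% at an assumed 71 prescriptions per hospital-survey. The number needed for 80% power rises from 41 to 45.

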Date, time and venue: the session will take a maximum of 30 minutes with 10 minutes of discussion/questions. Session date, time and venue will be informed to all doctors one week in advance and again 3 days before starting the session. The session will be run in each hospital separately after conducting point prevalence survey (PPS) of hospital antimicrobial use and after all doctors have completed survey form on AMS knowledge for baseline data. Verbal consent will be asked from participants to record participant's names, age, sex, working positions, departments, years of work and phone number onto the session registration sheet.

Instructor: The principal investigator of the study will be the session instructor. Training will be given in the format of a PowerPoint presentation, following by question and discussion.

Session material: paper versions of both adult and paediatric prescribing guidelines will be distributed to doctors who participate to this session. A handout of the introductory session (the same standard session for all hospitals) will also be provided.

Session details include introduction of the guidelines, objectives of guidelines, guidelines skeleton and how to use these guidelines, see details as below:

1. Introduction to the guidelines

This guideline is based on:

- existing Lao treatment guidelines
- current data on infectious disease pathogens and antimicrobial susceptibility patterns in Laos
- international antimicrobial prescribing/treatment guidelines (e.g. WHO, CDC, NICE, IDSA, Sanford)

- both Lao and international clinicians, international infectious diseases experts and microbiologists contributed to this guideline

2. Giving the purpose of the having these guidelines:

- To support therapeutic clinical decision-making of Lao clinicians
- To guide the reasonable use of antimicrobials to optimize cure and control antimicrobial resistance in Laos
- To promote the use of essential medicines registered with the Lao Food and Drug Department
- To diminish the cost of care for infectious diseases whilst ensuring optimal treatment
- To promote patient safety by diminishing risks of allergy or toxicity
- To promote the use of microbiology laboratory techniques for infectious disease diagnoses and for guiding treatment

3. Explanation of overall guideline skeleton

- Therapeutic section
- Prophylactic section
- AMS section
- References
- Contact details

4. How to use these guidelines

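### The primary model counts the pre-guideline month-0 survey as paper reference and states no survey-round effect, so the app can be credited with the effect of introducing any guideline

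*Combined protocol and SAP*

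**What the plan says.** The Statistical analysis section, and the synopsis in the same terms, describe a logistic mixed model for adherence measured at months 0, 4, 8, 12 and 16. The intervention side runs from month 4 to month 16 and is compared "with all wedges in the reference arm from month 0 to month 12". Duration of exposure "will be included in the model as interaction term with the study arm", and clustering by hospital is adjusted for. No survey-round or calendar-time effect is written, and no third category for a period without a guideline.

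The timing of the month-0 survey is described as follows:

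- Section 3.5 b: the survey is done "to collect baseline data before introducing paper-based guidelines", and hospitals enter the reference period only once the paper version has been introduced.
- Pre-prescribing guidelines survey: it takes place "after the first round of PPS and before introduction of the paper prescribing guidelines".
- Appendix A6: the paper introductory session is held "after conducting point prevalence survey (PPS) of hospital antimicrobial use and after all doctors have completed survey form on AMS knowledge for baseline data".
- Figure 2: the month-0 cells show survey and report only. Paper first appears at month 4.
- Section 3.3 says the opposite: "one baseline measurement after introduction of the paper-based prescribing guidelines".

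The plan's own counts leave month 0 out. Section 3.3 speaks of "four outcomes measurements in total (excluding baseline measurement at start", and section 3.4 states: "This will give 1:1 ratio of intervention vs reference period of observation".

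**The concern.** The primary objective is app versus paper. If prescriptions agree less with the new guideline before it exists on the wards than after the paper copy arrives, pooling month 0 with paper lowers the reference. Part of the step from no guideline to any guideline then appears as an app effect.

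The missing round effect is a second route to the same error. In a stepped wedge, app surveys fall later than paper surveys, so arm is confounded with time. The protocol itself names possible sources of drift: a feedback report after every survey, another AMR programme starting at the same time in three of the six hospitals, and Ministry stewardship training. The result could be a false positive, or a real effect that is overstated.

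**Working it through.** **1. Exposure by survey.** Section 3.5 c.3 and Appendix A7 put each crossover survey before the app session, so the crossing pair is still on paper at that survey. Hospitals per cell, from Figure 2:

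| Month | No guideline | Paper | App |
|---|---|---|---|
| 0 | 6 | – | – |
| 4 | – | 6 | – |
| 8 | – | 4 | 2 |
| 12 | – | 2 | 4 |
| 16 | – | – | 6 |

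Months 4–16 give 12 paper and 12 app hospital-surveys, which reproduces the stated 1:1 ratio. Counting month 0 as reference gives (6 + 12):12 = 18:12. The first app survey is month 8; month 4 is right only as the start of exposure.

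**2. Stated power.** The 80% in section 3.3 cannot be reproduced, because prescriptions per hospital-survey (m) are not given. I solved for m with the linear mixed-model stepped-wedge variance:

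- V = (1−ρ)σ²/m·I + ρσ²·J, with ρ = 0.05 and σ² = 0.375 × 0.625 = 0.234
- power = Φ(0.15/SE − 1.96), for 30% versus 45%, two-sided 5% (assumed)

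With round effects, 80% needs m = 41 (months 0–16) or 45 (months 4–16). Without them it needs m = 12 or 15.

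**3. Bias when the app does nothing.** Inputs: paper = app = 30% (section 3.3) and ICC 0.05. Month-0 adherence is unknown. The 13% in section 3.3 is from 2017 and older guidelines, so 13%, 20% and 25% are assumptions.

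Simple pooling at 13%: (6 × 13 + 12 × 30)/18 = 24.3%. The crude OR is (0.30/0.70)/(0.243/0.757) = 1.33.

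Fits to the expected cell proportions, with hospital effects and Figure 2 coding (true OR 1.00):

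| Month-0 adherence | Arm only | Round effects, month 0 kept or dropped |
|---|---|---|
| 13% | 1.38 | 1.00 |
| 20% | 1.20 | 1.00 |
| 25% | 1.10 | 1.00 |
| 30% | 1.00 | 1.00 |

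**4. False-positive rates.** Random-intercept logistic model, 300 simulated trials per setting, Wald test at 5%, Monte Carlo SE up to 2.9 points. The arm-only model rejects at:

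| Month-0 adherence | m = 40 | m = 75 | m = 100 |
|---|---|---|---|
| 13% | 66% | 89% | 94% |
| 20% | 23% | 41% | 57% |
| 25% | 10% | 15% | 21% |

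With round effects the rates are 3–6%. A separate run of 400 trials gave 58% (m = 35) and 95% (m = 100) for arm-only at 13%, and 4–8% with round effects.

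**5. The duration term.** Its form is not stated, and in all 18 reference cells duration equals calendar month. Simulated OR for app versus paper at equal duration, linear form (true value 1.00):

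| Month-0 adherence | 4 months | 8 months | 12 months |
|---|---|---|---|
| 13% | 1.41 | 0.96 | 0.66 |
| 20% | 1.21 | 0.97 | 0.78 |
| 25% | 1.11 | 0.98 | 0.87 |

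Categorical duration isolates month 0 and gives 1.00 at each duration when there is no trend. But it then sets app surveys only against paper surveys from earlier rounds: app at 4 months is observed at months 8, 12 and 16, paper at 4 months only at month 4.

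**6. Time trend alone.** Drop month 0, let the odds rise 10% per round, and give the app no effect. The arm-only and linear-duration models both give OR 1.21. With round effects the OR is 1.00.

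**7. A real effect.** 30% to 45% is OR (0.45/0.55)/(0.30/0.70) = 1.91. With month 0 at 13%, the arm-only fit to expected proportions gives 2.63; with round effects it gives 1.91.

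**The case against.** The strongest reply is that the sentence describes exposure intervals. If the intervention from month 4 means time on the app, the reference from month 0 means time on paper, observed at months 4, 8 and 12. That fits the 1:1 ratio, the four measurements without baseline, and the rule in section 3.5 b on when the reference period starts. This may well be what was intended. But the sentence before it lists month 0 among the measurements in the model, and a two-arm model offers no other place for it. The round-effect problem also remains under this reading (step 6).

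Second, the arm-only figures come from a simpler model than the plan's, which includes duration by arm. This is fair. Averaging the linear-duration ORs over the 6, 4 and 2 app surveys gives 1.09, 1.05 and 1.02 for month 0 at 13%, 20% and 25%, with false-positive rates of 3–18%. At 12 months the error goes against the app. What stands is that the result depends on a coding choice the plan does not make, and that single-duration contrasts stay biased.

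Third, month-0 adherence and m are assumed. That is true, so the sizes are illustrative only.

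Fourth, the plan cites a methods paper on stepped-wedge analysis beside the model sentence. A citation does not state which terms this trial will fit.

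**Conclusion.** The concern holds and must be fixed before analysis. The design can estimate app versus paper from months 4–16, but the written model does not ensure that it does. With arm and hospital only, a null app effect would appear as an OR of about 1.10 to 1.38 for month-0 adherence between 25% and 13%. There is no month-0 bias if adherence is already 30%. With linear duration the bias changes direction with duration. With month 0 removed, a 10% rise in odds per round still gives 1.21. The sizes rest on assumed month-0 adherence and assumed prescriptions per hospital-survey. The contradiction in timing and the absence of a stated round effect rest on the text alone.

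**What to change.** - Code exposure as in the table in step 1, with month 0 as no guideline.
- Estimate app versus paper from months 4–16, or keep month 0 only as its own round. In both cases add categorical survey-round effects.
- State the form of the duration term and restrict it to time on the app. With hospital and round effects, categorical duration in both arms is not fully estimable (design rank 14 of 16 columns); app duration alone is (13 of 13). The aim of assessing duration on paper has to be given up, because it cannot be separated from calendar time.
- State that the intervention from month 4 means exposure and that the first app survey is month 8.
- Correct section 3.3 so that baseline precedes the paper guideline, and align the synopsis.

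The cost is wording, with no new data. The SE of the log OR rises from about 0.10 to about 0.19 at an assumed 75 prescriptions per hospital-survey, where power for 30% versus 45% is still about 95%. That figure assumes hospital intercepts only, with no hospital-by-round variation. Dropping month 0 rather than keeping it as its own round raises the requirement for 80% power from 41 to 45 per hospital-survey. Month 0 still serves the before/after secondary objectives.
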